3.3 Centre Pools

Since this is a single centre study, pooling of centres is not applicable.

3.4 Time points and Visit Windows

The time points and visits for this study are defined in [Table 1-1](#), “Schedule of Activities”. Deviations from the scheduled assessment times should be avoided or kept to a minimum as far as possible. Any deviation from the study schedule may be reviewed on a case-by-case basis at the Blinded Data Review Meeting (BDRM) before database lock to determine whether the data should be excluded from the analysis populations. A time window non-compliance listing will be produced for the BDRM.

All data included will be by nominal visits and visit windows will not be considered.

4 Data Analysis

Syneos Health will perform data analysis with oversight from GSK CH. The statistical analysis software used will be SAS (Studio) version 9.4 or higher.

Prior to database closure a BDRM will be conducted in which various aspects of the trial will be discussed and agreed. In addition, the assessment of any subjects who may have dropped or discontinued from the study due to Coronavirus Disease of 2019 (COVID-19) pandemic related events and the potential need of a sensitivity analysis will be discussed during BDRM. Any major changes to planned analyses will need an amendment to RAP.

Experimental Dentifrice: 67% w/w sodium bicarbonate, 0.2% w/w high molecular weight sodium hyaluronate and 0.221% w/w sodium fluoride

208175

Final Version 1.0 Statistical Reporting and Analysis Plan Text (Amendment 1),
10 Jun 2021

Unless otherwise described, all listings will be produced on all randomized subjects.

4.1 Populations for Analysis

4.1.1 Subject Disposition

Screen failures are defined as subjects who consent to participate in the clinical study but are not subsequently randomized. An enrolled subject is a subject who has signed informed consent and is eligible to proceed beyond the screening visit.

The number of subjects screened, enrolled and randomized will be presented in CCI [REDACTED]. The number and percentage of screen failure subjects (subjects not randomized) with reasons why subjects are not randomized will also be displayed. Percentages for screen failure subjects will be based on the total number of subjects screened.

The number and percentage of subjects who complete and discontinue the study, broken down by reason for discontinuation, will be presented by study product group and overall in CCI [REDACTED]. The percentages will be based on the number of subjects randomized.

CCI [REDACTED] will also present the number and percentage of subjects in each of the defined analysis populations by study product group and overall. Percentages will be based on the number of subjects randomized in the relevant study product group or overall.

Subject disposition including demographic data (age, sex and race), screening date, washout product start date and time, the subject status (completer, Yes/No), study completion/withdrawal date, duration (in days) in the study (defined as [(date of completion or withdrawal – washout product start date) + 1], the primary reason for withdrawal and further details for withdrawal will be listed CCI [REDACTED] for all randomized subjects.

Subject disposition information will be listed for non-randomized subjects (CCI [REDACTED]), including demographic information (age, sex and race), screening date, reason for screen failure and any further details of reason for screen failure.

4.1.2 Protocol Deviations

Protocol deviations will be tracked by the study team throughout the conduct of the study. Data will be reviewed prior to unblinding and closure of the database to ensure all important deviations are captured and categorized.

Important deviations of the protocol procedures may include, but will not be necessarily be limited to the following:

- Violation of inclusion or exclusion criteria
- Non-compliance with study product use
- Use of prohibited treatment or medication before or during the study

Experimental Dentifrice: 67% w/w sodium bicarbonate, 0.2% w/w high molecular weight sodium hyaluronate and 0.221% w/w sodium fluoride

208175

Final Version 1.0 Statistical Reporting and Analysis Plan Text (Amendment 1),
10 Jun 2021

- Violation of visit windows

Subjects with important protocol deviations liable to influence the efficacy outcomes will be excluded from the PP population. Subjects may also be identified as having important protocol deviations not leading to exclusion from the PP population. The specific details of the important protocol deviations and how these will be assessed will be specified in the Blind Data Review (BDR) Plan with reference to the Protocol Deviation Management Plan (PDMP). Subjects with important protocol deviations will be identified at the BDRM. The BDRM will be conducted in a manner to ensure that the study statisticians and clinical research scientist remain blinded to every extent possible. Further details regarding maintaining the blindness during the BDRM will be described in the BDR Plan.

The number and percentage of subjects with at least one important protocol deviation, important protocol deviations not leading to exclusion from PP population with reasons for deviations and subjects with important protocol deviations leading to exclusion from the PP population with reasons for deviations will be presented by study product group and overall (CCI [REDACTED]) and listed (CCI [REDACTED]) for all randomized subjects.

All protocol deviations collected on the protocol deviation case report form (CRF) will be listed in CCI [REDACTED]. The listing will present date of deviation, type of deviation and deviation description.

4.1.3 Analysis Populations

The analysis populations defined for this study are as follows:

Table 4-1 Analysis Populations

Population	Definition/Criteria	Analyses Evaluated
Safety	All randomized subjects who receive at least one dose of the study product. This population will be based on the study product the subject actually received.	Safety
Modified Intent-To-Treat (mITT)	All randomized subjects who received at least one dose of the study product and provided at least one post-baseline assessment of efficacy. All mITT population summaries and analyses will be presented according to the study product randomized.	Efficacy
Per Protocol (PP)	All randomized subjects who are part of mITT population and fully comply with all study procedures and restrictions. Subjects with a protocol violation that is deemed to affect efficacy for only some (but not all) of the efficacy assessments will be part of the PP population, but their data will be	Efficacy analyses for BI score

Experimental Dentifrice: 67% w/w sodium bicarbonate, 0.2% w/w high molecular weight sodium hyaluronate and 0.221% w/w sodium fluoride

208175

Final Version 1.0 Statistical Reporting and Analysis Plan Text (Amendment 1),
10 Jun 2021

Population	Definition/Criteria	Analyses Evaluated
	excluded from the assessment at which the protocol violation occurred.	
MGI Repeatability	Subjects with at least one initial and repeat assessment of MGI at any visit.	Repeatability analyses
TPI Repeatability	Subjects with at least one initial and repeat assessment of TPI at any visit.	Repeatability analyses

The primary population for assessment of efficacy will be the mITT Population. A PP analysis will be performed only on the primary efficacy variable (NBS), if more than 10% of subjects in the mITT population are excluded from the PP Population.

Any repeat clinical data collected for the repeatability assessment will only be used to assess repeatability. The main assessment of efficacy will be based on the initial efficacy assessments.

The numbers of subjects included in each of the analysis populations will be presented in CCI [REDACTED] by study product group and overall. Subjects excluded from any of the analysis populations will be listed in CCI [REDACTED] by study product group.

4.2 Subject Demographics and Other Baseline Characteristics

4.2.1 Demographic Characteristics

Descriptive statistics (number of subjects [n], mean, standard deviation [SD], median, minimum and maximum for continuous variables, frequency count [n] and percentage [%] for categorical variables) will be presented for demographic characteristics by study product group and overall. These variables include gender, race, and age (years) which will be presented for the Safety population (CCI [REDACTED]), the mITT population (CCI [REDACTED]) and if applicable, for the PP population (CCI [REDACTED]).

Demographic characteristic information will be listed for all randomized subjects in CCI [REDACTED].

4.2.2 Baseline Characteristics

Descriptive statistics will be presented for baseline characteristics by study product group and overall. These variables include Mean BI, Mean MGI, Mean TPI, Stratification factors (gender and high/low number of bleeding sites), and will be presented for the Safety population (CCI [REDACTED]), the mITT population (CCI [REDACTED]) and if applicable, for the PP population CCI [REDACTED]).

Experimental Dentifrice: 67% w/w sodium bicarbonate, 0.2% w/w high molecular weight sodium hyaluronate and 0.221% w/w sodium fluoride

208175

Final Version 1.0 Statistical Reporting and Analysis Plan Text (Amendment 1),
10 Jun 2021

Baseline characteristic information will be listed for all randomized subjects in **CCI** [REDACTED].

4.2.3 General Medical History

Medical history data will be listed (**CCI** [REDACTED]) for all randomized subjects with start date and end date or ongoing at the start of the study.

4.3 Treatments (Study Product, Other Concomitant Therapies, Compliance)

Randomization details will be listed, including the randomization number, stratification group, the planned randomized product, the actual study product the subject received and the randomization date (**CCI** [REDACTED]).

The study product kit allocations also will be listed, including kit list number and study product information (**CCI** [REDACTED]).

4.3.1 Study Product Compliance and Exposure

Product compliance will be measured as number of missed brushings since last visit and number of additional brushings since last visit.

Compliance will be calculated for each visit interval and overall as:

- Compliance (%) = (Actual number of brushings / Expected number of brushings) x 100.

Where:

- Expected number of brushings = (Date of Visit_n – Date of Visit_{n-1}) x 2.
- Actual number of brushings = Expected number – missed brushings + additional brushings.

A threshold of compliance with allocated study product has been set as 80% of the recommended doses. Subjects with overall compliance <80% will be considered protocol deviations and assessed at the time of BDRM for exclusion from the PP population.

The number of missed brushings, additional brushings and percentage compliance (as continuous variable and by groups [< 80%; between 80% and 120%; > 120%]) will be summarized by study product group for each visit interval and for overall study product duration, in **CCI** [REDACTED] for the mITT population.

Exposure to study product will be calculated for each visit interval and overall study product duration as follows:

- Exposure (Days) = Date of Visit_n – Date of Visit_{n-1}.

Experimental Dentifrice: 67% w/w sodium bicarbonate, 0.2% w/w high molecular weight sodium hyaluronate and 0.221% w/w sodium fluoride

208175

Final Version 1.0 Statistical Reporting and Analysis Plan Text (Amendment 1),
10 Jun 2021

Product exposure (days) will be summarized by study product group for each visit interval and for overall study product duration, in **CCI** [REDACTED] for the mITT population.

Compliance and exposure data will be listed for all randomized subjects (**CCI** [REDACTED]).

Overall exposure and compliance will be calculated for Baseline (Visit 2), Day 3 (Visit 3), Week 1 (Visit 4), Week 2 (Visit 5) and Week 6 (Visit 6).

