4.6 Analysis of Safety

All safety data will be reported for the Safety population as per actual study product received. The safety profile of the study products will be assessed with respect to AEs, incidents, Oral Soft Tissue (OST) examination and Oral Hard Tissue (OHT) examination.

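### Exposure is summarised only for the mITT population and only from visit dates, so a treated subject with no post-baseline efficacy assessment counts in the adverse event tables but not in the exposure summary

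*SAP*

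**What the plan says.** SAP section 4.3.1 summarises product exposure in days "by study product group for each visit interval and for overall study product duration, in CCI [REDACTED] for the mITT population". The only formula is "Exposure (Days) = Date of Visit_n – Date of Visit_{n-1", the difference between consecutive visit dates. No first-use or last-use date enters it, and overall exposure has no formula of its own. The section adds a listing: "Compliance and exposure data will be listed for all randomized subjects".

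Table 4-1 in SAP section 4.1.3 defines the Safety population as "All randomized subjects who receive at least one dose of the study product", grouped by the product received. It defines mITT as "All randomized subjects who received at least one dose of the study product and provided at least one post-baseline assessment of efficacy", grouped by the product randomized. For safety, SAP section 4.6 says: "All safety data will be reported for the Safety population as per actual study product received".

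Protocol sections 4.1 and 8.2.1 place the first use of study product at a supervised brushing on site at the Baseline visit. The first scheduled post-baseline efficacy assessment is at Day 3 ± 1.

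**The concern.** The safety objective is oral tolerability over 6 weeks of twice-daily use, with treatment-emergent adverse events as its endpoint. A reader judging those tables wants to know how long the same subjects used the product. The plan answers that question for a different set.

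The two sets differ by exactly the treated subjects who have no post-baseline efficacy assessment. Almost by definition these have very little documented exposure, and early intolerance is one plausible reason for leaving. The exclusion can therefore move the exposure summary in one direction only. The two displays also use different grouping rules, product randomized for exposure and product received for safety.

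A lesser point follows from the formula. A subject who stops brushing but attends a later visit is credited with days up to that visit.

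**Working it through.** **1. The plan's own figures.** SAP section 1.4 (and protocol section 12.1) gives 36 evaluable per group at Week 6 with 10% drop-out. 36 / (1 − 0.10) = 40 per group and 108 / (1 − 0.10) = 120 in total, so both stated numbers reproduce. The allowance is 40 − 36 = 4 subjects per group, and it covers all losses up to Week 6. The plan states no exposure figure to reproduce.

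**2. A subject dosed on Day 0 with no post-baseline visit.**

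| Display | Requirement | Included? |
|---|---|---|
| Adverse event tables (Safety, product received) | one dose | yes |
| Exposure summary (mITT, product randomized) | one dose and one post-baseline efficacy assessment | no |
| Exposure listing (all randomized) | randomization | yes, but the value is undefined |

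The value is undefined because the formula needs a visit after Baseline and there is none.

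**3. Size, as an illustration.** Let N be the treated subjects in an arm and k those with no post-baseline assessment.

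Overstatement of the mean = (k / N) × (mITT mean − mean of the k excluded).

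Assumptions: N = 40, the k subjects have 1 day each, and all others have 42 days. The mITT mean is then 42.0, and the Safety mean is [(40 − k) × 42 + k] / 40.

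| k | Share of arm | Safety mean (days) | Overstatement (days) |
|---|---|---|---|
| 0 | 0% | 1680 / 40 = 42.0 | 0 |
| 1 | 2.5% | 1639 / 40 = 40.98 | 1.0 |
| 2 | 5% | 1598 / 40 = 39.95 | 2.05 |
| 4 | 10% | 1516 / 40 = 37.90 | 4.1 |

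The documents do not give k. The last row puts the whole drop-out allowance before the Day 3 assessment and is an extreme bound.

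**4. Sensitivity to the assumption that the rest complete.** Suppose one of four drop-outs leaves before Day 3 and the other three leave after the Day 14 visit. The mITT mean is (36 × 42 + 3 × 14) / 39 = 1554 / 39 = 39.85, with a minimum of 14 days. The Safety mean is (1554 + 1) / 40 = 38.88. The overstatement is 0.97 days. Later drop-outs do appear in the mITT summary; only the earliest are lost.

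**The case against.** Much of the information is reported elsewhere. Exposure is listed for all randomized subjects. SAP section 4.1.1 tabulates discontinuations by reason and product group with randomized subjects as the denominator, and lists the withdrawal date and reason. SAP section 4.6.1 lists adverse events leading to discontinuation. An early leaver with mouth irritation would be visible. This stands, but a listing is not a summary by arm. The days-in-study figure in that listing starts at the washout product, so it does not replace study-product exposure.

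The point about stopping product while still attending is largely covered. Missed brushings and percentage compliance are summarised by interval and overall in the same section, so such a subject would show low compliance.

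The exposure table feeds no safety result. Neither document plans an exposure-adjusted event rate, and SAP section 4.3 places exposure beside compliance, which protocol section 12.2.4.1 assigns to mITT. This also stands and keeps the point small. That protocol section ties only compliance to mITT, however, so moving exposure contradicts nothing there.

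The difference in grouping matters only after a dispensing error. Allocation is by interactive response technology (protocol section 6.5), a second staff member checks dispensing (6.1.2), and planned and actual product are both listed (SAP section 4.3).

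Finally, the list of data displays in SAP Attachment 1 is redacted. A further exposure table for the Safety population cannot be ruled out, although the SAP text describes none.

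**Conclusion.** The point holds as a minor one. The only exposure summary that the SAP text describes leaves out treated subjects with no post-baseline efficacy assessment and gives no exposure value to a subject with no visit after Baseline. The adverse event tables count them. Relative to the treated set, mean exposure can only be overstated. On the assumptions above the overstatement is about 1 day per arm for one such subject and about 2 days for two. It is zero if there are none, which the documents leave open.

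A reader might infer more, and the documents do not support it:

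- That exposure is reported only by visit interval. Overall duration is summarised too; the limitation is that both rest on visit dates alone.
- That tolerability results are biased. Event counts and denominators use the Safety population and are untouched, as is the primary analysis.
- That the distortion is greatest in the worst-tolerated arm. This is possible, but the plan gives no early-loss rate by arm.
- That the reported minimum would be about 42 days. This follows only if every remaining subject completes, as the sensitivity case shows.

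**What to change.** In SAP section 4.3.1, summarise exposure for the Safety population by product actually received, and leave compliance on mITT. Define overall exposure as follows:

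- Where the diary gives a last-use date: last use date minus first use date + 1. If the last brushing is on the evening before a Day 42 visit, this gives 41 − 0 + 1 = 42 days, matching the visit-date formula.
- Otherwise: use the last attended visit date in place of the last-use date, and state whether the extra day is added.
- With neither a post-baseline visit nor a diary date: 1 day, for the Day 0 supervised brushing.

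The cost is one re-based table. The SAP already tabulates demographics and baseline characteristics for the Safety population and records the product received. The main downside is the last-use date. Protocol section 6.2 has subjects record the date and time of each brushing in the diary, but section 6.7 specifies transcription to the CRF only for the number of missed or additional applications. The date may have to be taken from the diary, and it will be missing for some early leavers, for whom the fallback applies.

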4.3.2 Prior and Concomitant Medication

Any medications, treatments or vaccine (including over-the-counter or prescription medicines, vitamins and/or herbal supplements) taken during the study, from signing the informed consent, must be recorded in the CRF with indication, reason for use, unit dose, daily dose and start/stop dates of administration. All subjects will be questioned about concomitant medication/treatments at each site visit.

The prior and concomitant medications will be coded using an internal validated medication dictionary, **CCI** [REDACTED].

Prior medications are defined as those taken within 30 days of signing the informed consent form. If the stop date is unknown or incomplete and the medication cannot be considered as stopped prior to the first use of study product, then the medication will be considered as a concomitant medication.

Prior medication will be listed by subject, with drug name, GSK drug synonym, reason for medication, dose, frequency, route, start date, study day relative to first use of study product and end date (**CCI** [REDACTED]) for all randomized subjects.

Concomitant medications and significant non-drug therapy will be listed similarly (**CCI** [REDACTED]) with either ongoing or end date displayed. Concomitant medications are defined as medications that started or stopped on or after the date of first use of the study product, or are ongoing. In this study, any medications recorded after signing the ICF will be considered a concomitant medication.

Unknown dates will not be imputed, however if the start or stop date is unknown, then it will be assumed to be concomitant medication unless the partial start date or stop date indicates differently.

4.4 Analysis of Efficacy

The analysis of primary and secondary efficacy variables will be based on the initial assessment. The mITT population will be considered as primary population for efficacy analyses.

Experimental Dentifrice: 67% w/w sodium bicarbonate, 0.2% w/w high molecular weight sodium hyaluronate and 0.221% w/w sodium fluoride

208175

Final Version 1.0 Statistical Reporting and Analysis Plan Text (Amendment 1),
10 Jun 2021

4.4.1 Primary Efficacy Endpoint

4.4.1.1 Primary Efficacy Endpoint Definition

The primary time point is week 6 and primary comparison is between the 67% w/w sodium bicarbonate, 0.2% w/w HMW sodium hyaluronate and 0.221% w/w sodium fluoride (Experimental Dentifrice) and the fluoride control dentifrice (Negative Control Dentifrice).

The primary efficacy variable is the NBS and will be derived from the BI, whereby a site will be considered bleeding if the bleeding index score is 1 or 2 and will be considered not bleeding if the bleeding index score is 0.

The BI scoring system will be as follows:

Table 4-2 The Bleeding Index (BI)

Score	Description
0	Absence of bleeding on probing
1	Bleeding observed within 30 seconds of probing
2	Bleeding observed immediately on probing

As there is, only a single primary objective no adjustment for multiple comparisons is required.

The BI is assessed on the facial and lingual gingival surfaces of each scorable tooth. Three scores (according to the scale below) are recorded buccally/labially (distal, body, mesial sites) and three scores lingually/palatally. All scorable teeth in one quadrant are probed for approximately 30 seconds before recording the number of gingival units, which bleed.

Descriptive statistics (n, mean, SD, standard error [SE], median, minimum, maximum) of the primary variable will be provided at Baseline, Day 3 (Visit 3), Week 1 (Visit 4), Week 2 (Visit 5) and Week 6 (Visit 6) by study product group for the mITT population (CCI [REDACTED]).

The mean and SE of the NBS for each study product group will be presented graphically over time for the mITT population in CCI [REDACTED].

The BI obtained for each site along with the details of whether or not the site was bleeding (i.e. 'Yes' if BI score for a site is 1 or 2) and total number of bleeding sites will be listed by subject and visit in CCI [REDACTED] for all randomized subjects.

